As physical exercise can increase multifidus muscle performance and it has beneficial impact in MS, we propose a pilot study to evaluate the feasibility of a home-exercise program for the diagnosis and treatment of low back pain in MS patients focused on the multifidus muscle. If shown to be feasible, this novel tool can be taught in person or in online appointments, adding to the care of MS patients.

Specific Aims

We propose a pilot study to evaluate the feasibility of a home-exercise program for the treatment of low back pain in MS patients that are not pregnant or do not have a prior diagnosis of lumbar radiculopathy or fibromyalgia. This novel tool would target the multifidus muscle and could be taught in person or in online appointments.

Aims/Objectives

- Primary aim: study the feasibility of a home-exercise program in patients with MS younger than 50 years old with expanded disability status scale (EDSS) between 1.5 to 5.5.⁸ Feasibility will be evaluated by the percentage of patients that finish the study as also by the compliance measured in hours with the home-exercise program.
- Secondary aim: qualify the multifidus dysfunction in patients with MS through evaluation of the cross-section area of the multifidus muscle measured by ultrasound at the beginning and end of the study, and by physical exam maneuvers (multifidus lift and prone instability tests).

Title: Pilot Project for Multifidus Muscle Evaluation in Patients with Multiple Sclerosis and Back Pain
PI: [name] [name]
Institution: University of Arkansas for Medical Sciences

- Exploratory aim: Evaluate the relation between compliance with the home-exercise program and the change in the cross-section area of the multifidus muscle and the change in pain score using PROMIS scale.⁹

Study Design and Procedures

This is a prospective pilot project to evaluate the feasibility of a home-exercise program to improve the function of the multifidus muscle with the intention to decrease back pain in patients with Multiple Sclerosis. Figure 1 summarizes the study design and procedures.

[figure not shown]

Figure 1

PROMIS: Patient-Reported Outcomes Measurement Information System, US : ultrasound, PE: Physical exam, PT: physical Therapy.

Adult patients with MS and back pain, further described in the study population section, will be asked to participate in this study during an appointment with their neuro-immunologist. It is standard of care to refer patients with back pain to the pain clinic.

After patient consent at the neuro-immunology appointment, the study participant will be contacted by UAMS Pain clinic staff for an appointment. In that appointment, the participant will fill PROMIS scale that evaluates patient's quality of life, depression symptoms and pain levels. It is standard of care to ask patients regarding pain and how pain affects their mood and their daily life. In this study, we are standardizing those questions with PROMIS scale.

Next, the participant will undergo a physical exam that will include standard of care physical exam plus physical maneuvers that evaluate multifidus muscle performance. After that, a physical therapist, who is a pain clinic staff, will teach a series of exercises focused at this muscle. This is not standard of care, and it is specific for the patients that are enrolled in this study.

Title: Pilot Project for Multifidus Muscle Evaluation in Patients with Multiple Sclerosis and Back Pain
PI: [name] [name]
Institution: University of Arkansas for Medical Sciences

On the same day, an ultrasound will measure the cross-section of the multifidus muscle. It is standard of care for patients in the pain clinic undergo ultrasound, for the participants in this clinical trial, we will include the multifidus muscle measurements.

After 3 months of home exercise, but not more than 4 months from the consent, the patient will return to repeat the same evaluations, with the same staff.

Office visits (including physical exam, ultrasound and the PROMIS scale) and physical therapy services are considered routine care for this patient population. Data will be collected from patient medical record for research.

The study will be closed for recruitment after ten patients complete the final assessment. Data analysis will then start. Medical charts will be reviewed in all patients that gave consent. The review of the medical charts will finish after one year of study enrollment. Therefore, patient participation will be less than 2 years.

Study Population

Patients following in the two neuro-immunology clinics at UAMS will be recruited to this study. It is protocol in the neuro-immunology clinic to ask patients with MS about pain. An email to other UAMS neurologists as also neurologists that are outside of UAMS will be sent to advertise that UAMS will be providing this pilot project. If their patients want to participate to this program, a referral will be needed for those patients to be seen in the neuro-immunology clinic.

The study population will comprise of adult patients with MS who have back pain and that are following at the neuro-immunology clinic at University of Arkansas for Medical Sciences (UAMS). We anticipate including up to 10 participants in this pilot study.

Inclusion criteria:

- confirmed diagnosis by an UAMS neuro-immunologist of relapsing-remitting MS or primary progressive MS or secondary progressive MS
- Age between 18 years old and 50 years old on consent
- Complain of low back pain or severe axial back pain
- English-speaking

Exclusion Criteria:

- Patients that also have the diagnosis of thoracic or lumbar radiculopathy or history of prior thoracic or lumbar spinal surgery.
- Patients that are currently pregnant.

Title: Pilot Project for Multifidus Muscle Evaluation in Patients with Multiple Sclerosis and Back

Pain

PI: [name] [name]

Institution: University of Arkansas for Medical Sciences

- EDSS over 5.5 or less than 1.0
- Patient younger than 18 years old or older than 50 years old
- Knee total extension of less than 100 degrees

Risks and Benefits

A risk to study participants is the potential for loss of confidentiality of study data.

Measures to protect the confidentiality of study data will be implemented as described in the Data Handling and Recordkeeping section below.

Another potential risk is discomfort during the home-exercises. This will be low-risk. All exercises are low impact, and they will be taught by a physical therapist and can be reviewed and any moment through an app that patient will download.

Potential benefits include decrease in low back pain and improve in stabilization of the spine and in balance, as gait.

Data Handling and Recordkeeping

The Principal Investigator will carefully monitor study procedures to protect the safety of research subjects, the quality of the data and the integrity of the study.

When a participant enrolls in the study, a registration form will be completed by the physical therapist in their appointment. A study file containing the subject's name, medical record number, date of birth, sex, phone number, and address will be created. All study participant materials will kept at the Stephen's Spine Center. All questionnaires answered will be scanned into the participants' study files and electronic medical chart. Data will be collected from the patient's medical record.

A password-protected electronic file in a safe digital UAMS-maintained server will be used to store and manage data that include demographics, relevant personal information, diagnosis, current and prior treatments, and questionnaire results. The Principal Investigator, [name], will carefully monitor study procedures to protect the safety of research subjects, the quality of the data, and the integrity of the study. Six months after the study has been completed, information will be de-identified and stored in a safe digital UMAS-maintained server.

Data Analysis

Since this is a feasibility study, power analysis was not conducted.

Specific Aim 1: Primary aim: study the feasibility of a home-exercise program in patients with MS younger then 50 years old with expanded disability status scale between 1.5 to 5.5.

Title: Pilot Project for Multifidus Muscle Evaluation in Patients with Multiple Sclerosis and Back Pain
PI: [name] [name]
Institution: University of Arkansas for Medical Sciences

Data Analysis Strategy: Analysis will be descriptive. Feasibility will be evaluated by the percentage of patients that finish the study as also by the compliance in logged hours of exercise.

Specific Aim 2: qualify the multifidus dysfunction in patients with MS through evaluation of the cross-section area of the multifidus muscle measured by ultrasound at the beginning and end of the study, and by multifidus lift test and prone instability)

Data Analysis Strategy: As there is no literature in the evaluation of multifidus muscle in patients with MS, this will be a qualitative description of cross-section area and muscle performance on physical exam.

Specific Aim 3: Evaluate the relation between compliance with the home-exercise program and the change in the cross-section area of the multifidus muscle and the change in pain score using PROMIS Scale. Variables to also be considered will be EDSS of the patient.

Data Analysis Strategy: multiple linear regression will be used to evaluate if there is an association between the change in the multifidus cross-section area with compliance with home-exercise program, EDSS and pain level. ROC curve analysis will be done evaluating average hours of exercise per week and change in the cross-section area of a muscle.

This pilot project will end after 10 patients finish the home-exercise program of after one year.

Ethical Considerations

This study will be conducted in accordance with all applicable government regulations and University of Arkansas for Medical Sciences research policies and procedures. This protocol and any amendments will be submitted and approved by the IRB as required. Patients will not be compensated.

The formal consent of each subject, using IRB-approved consent forms, will be obtained before any study procedures. All subjects for this study will be provided a paper consent form describing this study in language understandable to the study population. Consent materials will provide sufficient information for subjects to make an informed decision about their participation in this study. The person obtaining consent will thoroughly explain what the subjects need to know about the study, including study requirements, study risks and benefits, and possible alternative treatment(s).

The consent process will take place during their neuroimmunology clinic appointment. Participation privacy will be maintained and questions regarding participation will be answered. No coercion or undue influence will be used in the consent process. This consent form must be signed by the subject. The participant will receive a paper copy of

Title: Pilot Project for Multifidus Muscle Evaluation in Patients with Multiple Sclerosis and Back

Pain

PI: [name] [name]

Institution: University of Arkansas for Medical Sciences

the signed consent form and the informed consent process will be documented in the research record.

Dissemination of Data

Results of this study may be used for presentations, posters, and publications. The publications will not contain any identifiable information that could be linked to a participant. The study will be listed on clinicaltrials.gov in accordance with FDA requirements. The final, anonymized dataset will be made publicly available at the clinicaltrials.gov website.

Title: Pilot Project for Multifidus Muscle Evaluation in Patients with Multiple Sclerosis and Back Pain
PI: [name] [name]
Institution: University of Arkansas for Medical Sciences

References

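### The same staff repeat the ultrasound with no masking described, so expectation bias can affect the area comparison in Aim 2 and, if the reader knows exercise hours, the Aim 3 slope (low priority)

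*Combined protocol and SAP*

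**What the plan says.** Under Study Design and Procedures, the first pain clinic appointment covers the PROMIS questionnaire, the physical exam and the exercise teaching. The scan is made at that visit: "On the same day, an ultrasound will measure the cross-section of the multifidus muscle". It is added to routine clinic ultrasound: "for the participants in this clinical trial, we will include the multifidus muscle measurements". The second assessment comes "After 3 months of home exercise, but not more than 4 months from the consent", when "the patient will return to repeat the same evaluations, with the same staff".

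The Data Analysis section uses area in two of the three aims:

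- **Aim 2** looks at area at the start and end of the study, and "this will be a qualitative description of cross-section area and muscle performance on physical exam".
- **Aim 3** uses multiple regression to look for an "association between the change in the multifidus cross-section area with compliance with home-exercise program, EDSS and pain level". In addition, "ROC curve analysis will be done evaluating average hours of exercise per week and change in the cross-section area of a muscle".

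The primary aim does not use area: "Feasibility will be evaluated by the percentage of patients that finish the study as also by the compliance in logged hours of exercise".

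Nowhere do the documents mention masking of the reader, storage of images, a reading procedure or reader repeatability. They do not say who reads the scans, or whether that person sees the exercise logs or the PROMIS answers.

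**The concern.** All participants are taught the exercises at the first visit, and there is no comparison group. Staff who scan the same patient three months later will know that this is the scan on which a gain is hoped for. They may also know the first reading, the pain score or the hours exercised. If the area reading involves judgement, such as where the muscle border lies, that knowledge can move it.

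Without a control group, a reader shift at the final visit cannot be told apart from a real gain in area. The plan also says that there is no literature on this muscle in MS, so it offers no outside benchmark that would expose a shift. A shift that grows with known compliance would produce the very association that Aim 3 looks for.

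**Working it through.** The plan states no alpha, effect size, SD or measurement error for area, so there is no figure of its own to reproduce. The check has two parts: which analyses a shift can reach, and how large the effect would be for assumed shifts.

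**Inputs.** From the documents: one group, up to 10 participants, two scans per patient, and an Aim 3 regression of area change on compliance, EDSS and pain level. Assumed: normally distributed change with SD 1, so that shifts are in SDs of the change; no true change; no true relation with hours; normally distributed hours.

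**1. Which analyses are reached**

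Write the observed change as Y = e + b + g(H), where e is the change without reader bias, b a uniform final-visit shift and g(H) a shift that depends on hours H.

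- *Aim 2 description:* b adds directly to every patient's change.
- *ROC analysis:* no cut-off for area change is given. For any fixed cut-off, b moves patients across it.
- *Aim 3 regression:* b is a constant and goes into the intercept. The slope on hours is biased only through g(H), which requires the reader to know or guess H. In a simulation at n = 10 (20,000 runs, three predictors), uniform shifts of 0.25, 0.5 and 1.0 SD left the mean slope on hours at 0 to within 0.004, with about 5% false positives.

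**2. Uniform shift, Aim 2**

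The share of patients who appear to gain area is Φ(b), with Φ the standard normal distribution function:

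| Shift b (SD) | Apparent gainers |
|---|---|
| 0 | Φ(0) = 50% |
| 0.25 | Φ(0.25) = 59.9% |
| 0.5 | Φ(0.5) = 69.1% |

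**3. Shift only for above-median exercisers, Aim 3**

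Let Y = e + d·1(H > 0), with H standard normal.

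- Cov(H, Y) = d·E[H·1(H > 0)] = d/√(2π) = 0.399d
- Var(Y) = 1 + d²/4
- r = 0.399d / √(1 + d²/4)

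At d = 0.5: 0.1995/√1.0625 = 0.1995/1.0308 = 0.19. At d = 1.0: 0.399/√1.25 = 0.399/1.118 = 0.36.

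**4. What that means with 10 patients**

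The two-sided 5% critical correlation is t/√(8 + t²) with t = 2.306 on 8 df: 2.306/√13.32 = 0.63. Both spurious correlations are well below it. In simulation of the three-predictor regression, with independent covariates standing in for EDSS and pain, false positives for hours rise from 5% to about 7% (d = 0.5) or 14% (d = 1.0). Under a different assumption, a uniform 0.5 SD shift plus a bias rising by 0.25 or 0.5 SD per SD of hours, the slope is off by that amount and false positives are about 9% or 20%.

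**The case against.** Having the same staff at both visits is a defensible choice, because it keeps between-operator differences out of the change. This stands, and the fix keeps it.

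A reader might infer that the arrangement inflates a 5% error rate. With 10 patients, a uniform shift of 0.25 or 0.5 SD would make a paired t-test of the mean change significant about 11% or 29% of the time. The plan contains no such test. Aim 2 is a qualitative description, and no alpha or efficacy claim is stated, so the plan has no error rate there to inflate. Those figures do not measure the harm to this study.

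A reader might also infer that bias does enter both aims. The documents support only that it can. That staff are unmasked is a sound inference from the one-group before-after design and the absence of any masking, but it is not written down. Whether the reader sees the exercise logs is not stated, and without that knowledge the Aim 3 slope is unaffected.

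The text says neither that area is traced by hand nor that images are kept, so the ease of re-reading is an assumption. Masked reading is also only a partial remedy: probe position, level and choice of frame stay with an unmasked operator, and the physical-exam tests are not covered. All of this stands. It narrows the point and lowers its priority, but does not remove it.

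**Conclusion.** The point holds as a limited one. The plan has the same staff repeat the scan in a single group and describes no safeguard against expectation. A reader shift can therefore distort the Aim 2 before-after description and any ROC grouping by area change. It can distort the Aim 3 compliance slope only if the reader knows or guesses hours.

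The true size cannot be taken from the documents. The ranges in the working rest on the assumed shifts, on normality and on no true effect. At this sample size even the larger assumed shift, 1.0 SD confined to above-median exercisers, would usually not produce a nominally significant slope. The main risk is a misleading description or estimate carried into later work.

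Completion and logged hours, the primary feasibility measures, are untouched. This is a cheap improvement of low priority to a secondary and an exploratory aim.

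**What to change.** Add a short reading procedure to Study Design and Procedures before scanning starts:

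- Keep the same operator at both visits. Save the images from each visit and check at the scan that they are usable.
- After the last final visit, have someone else on the study team remove name, date and visit from the images. The same reader then measures all of them in random order, before seeing exercise logs or PROMIS scores.
- Use these readings for Aims 2 and 3.
- State that image acquisition and the physical-exam tests remain unblinded.
- If images cannot be stored, state the lack of masking as a limitation when reporting Aims 2 and 3.

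**Cost.** At most 10 patients × 2 visits = 20 image sets, assumed to take a few hours of masking and re-reading. No extra assessor, visit or procedure is needed. The clinic workflow changes slightly, and area values are not available until the end. That fits the plan, which starts analysis only after ten patients have completed the final assessment.

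### The size and stopping rules conflict, and nothing says how participants still in follow-up count in the primary completion percentage

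*Combined protocol and SAP*

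**What the plan says.** The combined protocol and SAP sets the size and the end of the study in three places.

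- Study Design and Procedures: "The study will be closed for recruitment after ten patients complete the final assessment. Data analysis will then start". The unit is a completed final assessment, and no limit on enrolment is given.
- Study Population: "We anticipate including up to 10 participants in this pilot study". The unit is a participant included.
- Data Analysis, last sentence: "This pilot project will end after 10 patients finish the home-exercise program of after one year" (the second "of" evidently means or). The unit is a finisher of the exercise program. Only this rule has a time limit, and the start of the year is not defined.

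The final visit is timed as "After 3 months of home exercise, but not more than 4 months from the consent". For the primary aim, Data Analysis says: "Feasibility will be evaluated by the percentage of patients that finish the study as also by the compliance in logged hours of exercise". The analysis is descriptive, with no threshold.

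The nearest text to a denominator is in Study Design and Procedures: "Medical charts will be reviewed in all patients that gave consent". It is followed by "The review of the medical charts will finish after one year of study enrollment" and "Therefore, patient participation will be less than 2 years". These sentences concern data collection and duration. They do not define an analysis set or delay the analysis.

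**The concern.** A feasibility study expects some dropout, and any dropout sets the first two rules against each other.

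- **Cap of 10 holds.** One dropout means ten completers are never reached. The stated start of analysis then never occurs, and no other start is given.
- **Cap does not hold.** Recruitment stays open until the tenth completion. People who consented shortly before it have not had time to finish when analysis begins.
- **One-year limit.** It can cut people off in the same way under either reading, but only if it ends follow-up as well as recruitment. The text does not settle that.

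The percentage itself is also undefined. The numerator could be final assessments, program finishers or study finishers. The denominator could be everyone who consented in the neuro-immunology clinic, or only those registered later at the physical-therapy appointment (Data Handling and Recordkeeping).

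Completion is one of two primary feasibility measures, the other being logged hours. With no threshold and no test, the reported percentage is itself the result. The same patient behaviour could be reported quite differently depending on choices that have not been written down.

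**Working it through.** The plan has no power or precision calculation, so there is no figure behind the 10 to reproduce. The check is whether the rules agree with each other and how far the percentage can move.

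**Inputs from the documents:** 10 included; 10 completers; one year; final visit after 3 months of exercise and within 4 months of consent.

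**Assumptions (the documents give none of these):** completion p = 80% or 90%; consents arriving at random (Poisson) at r = 0.5, 1 or 2 per month; final visit uniform over 3 to 4 months from consent; dropout uniform over 0 to 3.5 months; the year counted from opening.

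**Step 1. Ten included against ten completed.** All 10 must finish, with probability p^10: 0.8^10 = 0.107 and 0.9^10 = 0.349.

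**Step 2. Ten-completer rule alone, p = 80%.** Mean time in follow-up is 0.8 × 3.5 + 0.2 × 1.75 = 3.15 months, so the number unfinished at the tenth completion is about 3.15r: 1.6, 3.2 and 6.3. The number consented is about 10/0.8 + 3.5r: 14.3, 16.0 and 19.5. The ratio 10/consented is about 70%, 63% and 51%. Simulation, averaging the percentage over trials, gives 72%, 64% and 53%.

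**Step 3. One-year limit also ending follow-up, p = 80%.** Hand check at r = 0.5, uncapped: 6 consented, 0.5 × 0.8 × (12 − 3.5) = 3.4 finished, and 3.4/6 = 57%.

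The simulated averages below (200,000 trials per cell) are for 0.5 / 1 / 2 consents per month.

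| Rule | Finishers over all consented, p = 80% | Same, p = 90% |
|---|---|---|
| Ten completers, no cap, no year limit | 72 / 64 / 53% | 79 / 70 / 57% |
| Year limit ends follow-up, no cap | 57 / 57 / 52% | 64 / 63 / 56% |
| Year limit ends follow-up, cap of 10 | 57 / 67 / 80% | 64 / 75 / 90% |

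In the last row at p = 80%, the mean number unfinished is 1.5, 1.3 and 0.04.

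**Step 4. Change the counting.** The table counts unfinished participants as non-finishers, which the plan does not instruct. Leaving out those still in follow-up gives 77% to 80% in every p = 80% cell (74% to 81% if dropout is all early or all late), and 88% to 90% at p = 90%.

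**Step 5. Follow everyone consented, p = 80%.** Average completion is 80% to 81% under either size rule at all three accrual rates.

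**The case against.** The strongest reply is that the low percentages need a reading and a counting rule that the plan does not state. The uncapped case sets aside the figure of 10 in Study Population, and the first row of the table also sets aside the one-year limit. With both applied and 2 consents per month, almost nobody is unfinished and the average is 80%. Leaving out the unfinished keeps the average close to the truth under every stop rule. The plan closes recruitment, not follow-up; it says analysis starts, not that it ends; and chart review covers everyone who consented. The three descriptions of finishing may be loose synonyms. Aim 1 has no threshold, and at this size the percentage is imprecise anyway.

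Much of this stands. The stop rule alone moves the percentage little; it matters in combination with the counting choice. Under a cap of 10, distortion needs accrual of about 1 per month or slower and a year limit that ends follow-up. The chart-review sentences leave room for later visits.

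Two things remain. The rules still contradict each other as soon as one person drops out, even if the figure of 10 is only an expectation. And the plan neither makes analysis wait for those in follow-up nor says how to count them.

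**Conclusion.** The concern holds and should be fixed. The conflict between the three rules is in the text and needs no assumption. With 10 included, the stated start of analysis is reached only 11% of the time at 80% completion, or 35% at 90%.

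The size of the effect on the percentage rests on assumed accrual, completion and dropout timing. At a true 80%, the ten-completer rule alone with 2 consents per month gives 53% or 77% on average, depending only on whether the unfinished are counted as non-finishers or left out. Across the rules and rates examined, counting them as non-finishers gives 52% to 80%. The stop combined with the counting choice is the main driver; accrual sets how many participants are affected. No hypothesis test is touched.

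**What to change.** 1. State one size and stop rule in all three sections: either 10 consented, or a target of ten completers with the figure in Study Population restated. The choice is the sponsor's.
2. Make the stop, including the one-year limit, apply to new consent only, and say when the year begins.
3. Follow everyone already consented to final assessment or dropout, at most 4 months from consent, before the primary analysis.
4. Define completion as final assessment done over all consented. Report it also among those who attended the training visit. Give x/N, ideally with an exact 95% interval (8/10 gives 44% to 97%).

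**Cost.** Protocol wording, and up to about 4 more months: if consent runs to month 12, the last outcome falls at month 12 + 4 = 16. If the year must be a hard end, closing consent at month 12 − 4 = 8 also leaves nobody unfinished, with fewer participants.

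The size choice matters for Aim 3. At 80% completion and 0.5, 1 and 2 consents per month, with consent to month 12:

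- 10 consented: about 4.7, 7.6 and 8.0 completers.
- Ten-completer target: about 6, 12 and 19 consented and 4.8, 9.4 and 15.3 completers, so at about 1 per month or faster the protocol must allow more than 10 participants.

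### Specific Aim 2 plans only a qualitative description of multifidus cross-section area, a number measured at both visits, so its level, paired change and spread need not be reported (minor, secondary aim)

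*Combined protocol and SAP*

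**What the plan says.** The secondary aim (Aims/Objectives, repeated under Data Analysis, Specific Aim 2) is to characterise multifidus dysfunction in two ways. One is the "cross-section area of the multifidus muscle measured by ultrasound at the beginning and end of the study". The other is a physical examination, made "by multifidus lift test and prone instability" testing.

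Under Study Design and Procedures, the first pain clinic visit includes the scan: "On the same day, an ultrasound will measure the cross-section of the multifidus muscle". After about three months of home exercise, "the patient will return to repeat the same evaluations, with the same staff". Each completer therefore supplies a baseline and a final area.

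The whole analysis strategy for Specific Aim 2 is that "this will be a qualitative description of cross-section area and muscle performance on physical exam". The reason given is the absence of literature on this muscle in MS.

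Specific Aim 3 (exploratory) then uses multiple linear regression to ask "if there is an association between the change in the multifidus cross-section area with compliance with home-exercise program, EDSS and pain level", together with an ROC analysis of weekly exercise hours and change in area.

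On numbers: "The study will be closed for recruitment after ten patients complete the final assessment", and "This pilot project will end after 10 patients finish the home-exercise program of after one year". The Study Population section anticipates at most ten participants. No power analysis was done.

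**The concern.** A cross-section area is a continuous measurement, and two per patient give paired numeric data. A qualitative description is a poor match for such data. Read literally, the report could say that the muscle looked small, or looked larger at the end, without giving an area, a change or any measure of variability.

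The authors' rationale points the other way. If no values exist for this muscle in MS, as the plan states, then the level and the SD, both of the area and of its change, are among the more useful things this pilot could hand to whoever plans the next trial. A reader given a verbal description alone could not set an apparent change against its uncertainty.

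**Working it through.** The plan states no figure for this endpoint (no SD, effect size, power or interval), so there is nothing to reproduce. The check is mainly of the text, followed by a short calculation of what a numeric summary could deliver.

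**1. Does any section commit to a numeric summary of the area?**
- *Specific Aim 1*: says its analysis is descriptive and names its measures (percentage finishing, logged exercise hours). These concern feasibility, not the area.
- *Specific Aim 2*: gives a qualitative description. No mean, median, SD, range, paired change or interval is named. The lift and prone instability tests fall under the same phrase, with no counts named.
- *Specific Aim 3*: each completer's change in area must be calculated, but only to enter a regression and an ROC analysis. Both address association. Neither obliges the report to give the typical area, the average change or its spread, and neither involves the two physical tests.
- *Dissemination of Data*: promises a public anonymized dataset but does not list its variables.

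No section of the available text fills the gap.

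**2. Does the stated reason support the method?** Without earlier MS data there is no reference value to test against and no basis for a powered comparison. That is a reason for no hypothesis test. Estimating a mean, an SD or a paired change needs no earlier literature.

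**3. Are there too few patients for a numeric summary?** The 95% t-interval for the mean paired change has half-width t(0.975, n − 1) × SD_change / √n. The documents give no SD, so the results are in units of SD_change.

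| Pairs n | Source of n | Calculation | Half-width |
|---|---|---|---|
| 10 | completers named in the plan | 2.262 / 3.162 | 0.72 SD |
| 8 | assumption | 2.365 / 2.828 | 0.84 SD |
| 6 | assumption | 2.571 / 2.449 | 1.05 SD |

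Fewer than ten pairs is plausible. If enrolment stops at ten participants, as the Study Population section suggests, any dropout leaves fewer than ten pairs. The one-year stop could also end the trial before ten have finished.

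For scale, assume equal SDs at the two visits and a between-visit correlation r, so that SD_change = SD × √(2(1 − r)). With 10 pairs the half-width in single-visit SDs is then 1.000 × 0.715 = 0.72 at r = 0.5, 0.632 × 0.715 = 0.45 at r = 0.8, and 0.316 × 0.715 = 0.23 at r = 0.95. The values of r are assumptions; the documents give none.

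The SD of the change would itself be imprecise. With 10 pairs and normal changes, its 95% interval (chi-square method) runs from 0.69 to 1.83 times the observed SD.

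The intervals are wide but usable. These figures describe what the proposed summary would deliver; they do not measure harm from the present wording.

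**The case against.** The strongest reply is that this is a word choice. The investigators may have meant descriptive: they apply the word to an ultrasound area, they use the change in that area as a number in Specific Aim 3, and their reason reads like a case for describing without testing. On that reading, all that is left is a short pilot plan that does not list its summary statistics. This reading is plausible and cannot be ruled out. But the same section uses the word descriptive under Aim 1 and names the measures there, while Aim 2 uses a different word and names none. On either reading no summary is specified.

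A second reply is that the consequence is hypothetical. Aim 3 forces the change to be computed and a public dataset is promised, so the numbers will probably exist and may well be reported. That stands as a limit on severity. It does not amount to a commitment to report the secondary aim numerically.

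A third reply is that an interval is a refinement in a pilot that disclaims power. Individual values with median and range would indeed cover much of the need. The interval costs nothing further and lets the reader see the imprecision, provided it is fixed in advance. Choosing between intervals after looking at ten or fewer changes would be unreliable, and could move the target from the mean to the median.

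A reader might infer something stronger: that the trial will not quantify the area, or that the secondary aim is lost. The documents do not support that. The area is measured at both visits and its change is used as a number, so the data to answer the aim will be collected.

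**Conclusion.** The point holds as a minor one, on a secondary aim. The plan names a method that does not suit a paired numeric measurement, and the reason it gives justifies the absence of a test but not the absence of estimates. Followed as written, the Aim 2 report need not contain the level, paired change or spread; this is what the wording permits, not a prediction of what will be published. The primary feasibility outcome is unaffected.

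The size of the shortfall cannot be expressed as bias or lost power, because Aim 2 plans no test. The half-width of about 0.72 SD of the change rests on ten complete pairs and roughly normal changes. The conclusion that the wording should be replaced rests on neither.

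**What to change.** In Data Analysis, Specific Aim 2, replace the qualitative description with a quantitative descriptive analysis without hypothesis tests, and state that the report will:

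- list each participant's baseline and final area, de-identified;
- for participants with both visits, give the number of pairs, and the mean (SD) and median (range) at each visit and for the paired change;
- give a 95% t-interval for the mean change, specified in advance and reported whatever the data look like, with a note that it assumes roughly normal changes (the individual values and medians let readers judge that);
- give baseline and final counts for the lift and prone instability tests, if they are scored as categories.

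This takes three or four sentences and needs no new data or procedure. The downside is a little more reporting work and intervals that will be wide, more so if fewer than ten patients return.
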